- Most recent mammography screening appointment information (date of screening mammogram and location of screening mammogram)

The EHR will be reviewed by the PI for:

- Health care provider notes from visit pertaining to a concerning mole (date of visit, notes from visit, diagnosis code of mole, plan of treatment and/or treatment)

HIPAA Authorization will not be obtained from skin check partners, as the study team will not be viewing their EHR.

QUALIFICATIONS TO CONDUCT RESEARCH AND RESOURCES AVAILABLE:

[name] has been a board-certified physician for over three decades and has conducted an NCI funded R01 and R21 of a similar nature. We will notify the Northwestern University IRB, our project officers, and NCI within 24-48 hours of any serious adverse event. All research assistants have CITI documents on file. Other resources. Lynn Sage Breast Center completes approximately 90,000 screening mammograms each year and Kishwaukee Hospital completes approximately 7,000 screening mammograms/year; therefore, there are adequate numbers of potential subjects to be identified by the EDW search. [name] has full-time research staff and voluntary medical students who fully support this research study at 100% effort. [name] also has weekly meetings with research staff to address any questions regarding the protocol, questions from research subjects, or study related procedures.

MULTI-SITE RESEARCH:

NA

REFERENCES

1. Guy GP, Jr., Thomas CC, Thompson T, et al. Vital signs: Melanoma incidence and mortality trends and projections - United States, 1982-2030. *MMWR Morb Mortal Wkly Rep.* 2015;64(21):591–596.
2. Global burden of disease cancer collaboration, Fitzmaurice C, et al. Global, Regional, and National Cancer Incidence, Mortality, Years of Life Lost, Years Lived With Disability, and Disability-Adjusted Life-Years for 29 Cancer Groups, 1990 to 2016: A Systematic Analysis for the Global Burden of Disease Study. *JAMA Oncol.* 2018;4(11):1553-1568.

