STU#: 00212165

PROTOCOL TITLE: Targeted Melanoma Detection with Skin Self-Examination During COVID-19 Restricted Physician Access

PRINCIPAL INVESTIGATOR:

[name]
Northwestern University Feinberg School of Medicine
Department of Dermatology
[name]
[name]
[contact]
[contact]

RESEARCH PERSONNEL:

[name], MS
[name], BS

STATISTICIAN:

[name]
Professor of Preventive Medicine
Northwestern University Feinberg School of Medicine

VERSION DATE:

April 2, 2020

NCT04420273

STUDY SUMMARY:

The purpose and overarching aim of this study is to reduce melanoma mortality by improving early detection of melanoma with skin self-examination among people who self-identify as being at risk. Self-management of melanoma detection with skin self-examination (SSE) depends on ready access to dermatologists when a concerning mole is detected. In March 2020, the Illinois stay at home order (COVID-19) removed ready physician access and prohibited non-essential health care. Additionally, there was uncertainty about when regularly scheduled health care would resume. This submission seeks to explore the feasibility of at-home non-invasive mole self-sampling for those with a concerning mole with the intention of providing recommendations about the need for the mole to be biopsied.

OBJECTIVES:

Aim 1: To assess the effectiveness of targeted melanoma detection (TMD) with SSE education delivered remotely to women who had a screening mammogram.

The effect of TMD with SSE education on a) SSE performance, b) identification of concerning moles, c) time between noticing a concerning mole, requesting a mole self-sampling kit and receiving health care, and d) SSE sustainability in comparison with controls will be assessed among women served by Northwestern Medicine in one rural community and one metropolitan community. Health care providers' (HCPs) clinical/pathologic assessment of concerning moles will be identified in the Northwestern Medicine electronic health record (EHR) system.

Exploratory Aim: To assess the feasibility of self-sampling concerning moles for gene assay.

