Since most melanomas are visible on the surface of the skin at a curable phase in their evolution, people can perform screening at home with the help of a partner. The annual prevalence of self-reported SSE in the general community ranges from 8 to 21%.²⁰ Women perform more SSE than men.⁷ Women self-detect more than half of melanomas and melanomas detected by women had better prognosis than those detected by men because they were identified at an earlier stage.⁸ The American Academy of Dermatology recognized that 6-50% of melanomas were self-detected;^{21,22} therefore, the Academy encourages self-advocacy thorough routine SSE and regular skin cancer screening for at-risk patients.²³ In a 20 year follow-up case control study of people newly diagnosed with melanoma in 1987-89, skin awareness was associated independently with a decreased risk of melanoma death (HR=0.46, 95% CI=0.28-0.75, $p<0.01$).²⁴ Currently, the median delay in diagnosis, is ~27 months.²⁵ Reports suggest melanomas get about 0.12 mm deeper per month with attendant increasing disease stage.²⁶ A 27-month delay in diagnosis may result in a 0.12 mm deep melanoma (Stage 1A) becoming a 3.24 mm melanoma (Stage 2B with greater risk of metastasis). Time to presentation for care is a key determinant of the patient outcome. Compared with other cancers, melanoma has the longest delays measured as the median time to patient presentation. One goal of this research is to reduce the time from a woman first noticing a “new or changing mole” to examination by a doctor.

Leveraging the Mammogram Screening Encounter.

In the US, women age 50 and older develop the habit of having regular screening mammograms.²⁷ From 50-59 years of age is also when melanoma incidence in women increases.²⁸ In Illinois, screening mammograms may be scheduled without a physician's order, thus, women who do not have regular care with HCPs may obtain mammograms. One of the innovations of our proposed study, as described below, is using the screening mammography encounter as an opportunity to educate women of all races and ethnicities at the point in their lives when melanoma is most likely to develop. In our pilot feasibility research, we leveraged mammogram screening encounters to reach women, who were not aware of their melanoma risk.⁴ Women, who are the nexus of familial communication of health information and social support in their own homes and

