Subjects in the intervention arm will monitor new and concerning moles for 4 months by doing monthly skin checks and partner-assisted skin checks (if applicable), record the scores on a scorecard provided in their SSE brochure, and complete the monthly online survey, which asks about changes in mole scores and potential anxiety associated with evolving moles. Subjects will also receive a monthly text message to their personal phone with SSE reminders.

If the subject indicates on their monthly survey or by communicating with the study team, in the form of an email and/or call, that the score of their mole has increased, three options on how to proceed will be offered to the subject. The three choices are as follows: a) continue monthly checking the mole for change, b) receive the mole self-sampling kit to obtain genetic analysis to guide the decision to seek health care, or c) seek an appointment with an HCP.

The mole self-sampling kit contains the materials, directions and a Fed Express or USPS Express mail envelop to overnight the kit to the DermTech laboratory.

Participants may request a kit by email or telephone call to the research team, who will send the kit by Fed Express or USPS Express mail. Within 3-5 business days, the DermTech laboratory will provide the results of the gene analysis online to the PI, [name], who will inform the participant with a written report stating:

- a) the mole is benign, and nothing further is needed or
- b) the mole needs to be biopsied.

If the initial sample has too few cells for analysis, then the participant will be invited to obtain another sample, instructions will be reviewed by telephone or by Facetime with the participant and an additional sample will be obtained.

Participants requiring a skin biopsy will be referred to a local HCP. The research team will develop a participant navigation system for triage to a local HCP, including surgical oncologists, dermatologists, and family practitioners. This triage system will be used to refer participants to schedule an appointment for the skin biopsy within 2-3 weeks. The genetic analysis of the mole will be provided in a letter to the HCP selected by the participant.

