If the option to see the HCP is selected, the research team will assist with locating one and will remind the subject that the HCP may not be available for some time. The study team will not cover the cost of seeing the HCP or cost of treatment recommended by the HCP. The non-payments details are explicitly stated in the consent document.

If the mole(s) requires a biopsy and/or treatment, the EHR will be reviewed to identify diagnosis codes of the mole and review HCP notes.

If throughout the 4 months of active engagement in skin self-examinations, a participant in the intervention arm indicates that they found a concerning mole on their skin check partner while performing a partner skin exam, an opportunity for the concerning mole of the partner to be self-sampled will be offered. For the self-sampling to occur, the subject (the skin check partner) would first be asked eligibility questions to ensure they are over the age of 18 and meet basic eligibility criteria. Once eligibility is established, the partner will be sent an electronic consent form, via REDCap, and complete and sign the form,

indicating they understand what is expected of them as a research participant and the information that was presented to them in the consent document. The same process will be followed for the skin check partner as is in place for the research subject.

Controls (Group 1) will receive a healthy lifestyle brochure and a healthy lifestyle postcard after consenting online and completing baseline assessments. After enrolling in the study, a baseline survey will populate in REDCap, and the subject will be able to download a healthy lifestyle brochure and the postcard reminder. Upon request, the brochure will be mailed. Each month, the subject will receive an email to complete the monthly survey and will receive healthy lifestyle text messages to their mobile phone. The survey they receive will mirror the survey of the SSE intervention arm; therefore, awareness of SSE will be expected to increase, and SSE may be initiated among controls. If a subject indicates that they have found a concerning mole on their monthly survey, the subject will be advised to reach out to their health care provider for further assessment. After completing the final monthly survey, controls will be offered the SSE brochure.

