In order to complete this research before the end of the grant (March 2021), we need to have IRB approval in early May, which will allow EDW to build the lists of eligible subjects. Then we will enroll subjects remotely in June-August 2020 and follow them for 4 months with online surveys (Oct-Dec 2020). Finally, the EHR of HCP visits will be reviewed about 3-4 months after the completion of the last online survey. This additional period of EHR review (Feb 2021- March 2021) gives subjects time to obtain an appointment with their HCP and have a biopsy, if needed.

INCLUSION AND EXCLUSION CRITERIA:

Inclusion Criteria:

- Adult women (aged 18 and older) having a screening mammogram with no upper age limit, who had a screening mammogram from January 1, 2019 to February 28, 2020.
- Able to read English
- Vision enough to read a newspaper
- Self-perception of their potential melanoma risk
- Willing to perform SSE with a skin check partner
- Willing to complete monthly surveys for 4 months and receive monthly text messages to personal mobile phone
- Have home Internet access and smartphone with data plan
- Have access to Federal Express or US Postal Service Express Mail to send mole self-sampling kits
- Willing to allow the research team access to their electronic health record to abstract physician assessment of concerning moles, biopsy results and treatment
- Willing to provide up-to-date email address, mailing address and telephone number

Inclusion criteria of skin check partner to have mole self-sampled

- Male or female over the age of 18 years
- Able to read English
- Vision enough to read a newspaper

Exclusion criteria

- Women under the age of 18 years

- Women overburdened with other co-morbid diseases, medical treatments (e.g., chemotherapy), or cognitive impairment (e.g., by a stroke) as determined by the PI.
- Previous participation in SSE research previously which may be a confounding variable in data analysis

Exclusion criteria of skin check partner to have mole self-sampled

- Male or female under the age of 18
- Unable to read English

VULNERABLE POPULATIONS:

This study will not include the participation of vulnerable populations

PARTICIPANT POPULATIONS:

Accrual Number:	Category/ Group:	Consented: Maximum Number to be Consented or Reviewed/Collected /Screened	Enrolled: Number to Complete the Study or Needed to Address the Research Question
Northwestern Medicine: Prentice Women's Breast Center	Women ≥ 18 years old	500	400

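### Provider visits and biopsies are traced only through the Northwestern Medicine EHR, although women in both arms may be seen elsewhere; the secondary outcome may be undercounted, possibly unequally by arm

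*Combined protocol and SAP*

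**What the plan says.** **Source.** Objectives, Aim 1 states that providers' "clinical/pathologic assessment of concerning moles will be identified in the Northwestern Medicine electronic health record (EHR) system". Study Timelines adds that "the EHR of HCP visits will be reviewed about 3-4 months after the completion of the last online survey". The Protected Health Information section lists the visit items that will be abstracted from the EHR. No other record source for visits or biopsies is described.

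**Who is enrolled.** The Inclusion Criteria ask for a screening mammogram and for the woman to be "Willing to allow the research team access to their electronic health record to abstract physician assessment of concerning moles, biopsy results and treatment". They do not ask where she receives other care. The Background section notes that in Illinois a mammogram can be booked without a physician's order, so that "women who do not have regular care with HCPs may obtain mammograms".

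**Route to care, intervention arm.** Study Interventions states "Participants requiring a skin biopsy will be referred to a local HCP" and "The research team will develop a participant navigation system for triage to a local HCP". The gene result goes to the provider whom the participant chooses. Under Procedures Involved, the team also helps women who opt for an appointment to find a provider.

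**Route to care, control arm.** Under Procedures Involved, a control who reports a concerning mole has no study navigation: "the subject will be advised to reach out to their health care provider for further assessment".

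**Survey.** Study Interventions describes "the monthly online survey, which asks about changes in mole scores and potential anxiety associated with evolving moles". Procedures Involved adds goal setting and partner reminders. Neither mentions provider visits.

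**Outcome and analysis.** The secondary outcome compares the arms on appropriate and inappropriate appointments and biopsies. The power section analyses it as whether a woman had any provider appointment during the study. The missing-data rules there are written for drop-out and SSE.

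**The concern.** A woman enters through one mammogram in the system but may take her mole to a provider outside it. Neither arm's route to care is confined to Northwestern Medicine. If the EHR is the only place where visits are looked for, an outside visit or biopsy can go unseen.

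Two consequences follow for the secondary outcome, and for the time-to-care measure listed with the fidelity measures:

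- **Equal loss in both arms** shrinks the observed rates and their difference, and costs power.
- **Unequal loss** biases the comparison. The arms reach care by different routes, and study navigation exists in only one of them, so the share of visits falling inside the system could differ. A difference in where care was obtained could then be read as a difference in care-seeking, or could hide a real one. A larger sample does not cure this.

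**Working it through.** **Inputs from the plan (Design, Analysis, and Power Calculation):** about 500 per arm; appointment rate 14%; detectable control rate 21%; 80% power. I read 14% as the intervention rate and 21% as the control rate.

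**Assumptions of mine:** two-sided 5% (the plan states no alpha), a simple two-proportion comparison, and the shares of visits visible in the EHR. The documents give no capture share.

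**Formula.** With n per arm, d = |p1 − p2| and p̄ the mean rate:

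- s0 = √(2p̄(1−p̄)/n)
- s1 = √((p1(1−p1)+p2(1−p2))/n)
- power ≈ Φ((d − 1.96·s0)/s1)

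**Step 1: reproduce the plan's figure.** For 14% vs 21%, d = 0.070, s0 = 0.02403 and s1 = 0.02393. Then (0.070 − 0.0471)/0.02393 = 0.957, so power is 83.1%. Subtracting a continuity correction of 1/500 from d gives 80.9%. The control rate detectable with 80% power is 20.7% (20.9% with the correction), which rounds to the plan's 21%. The plan's figure holds if every appointment is captured.

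**Step 2: equal capture in both arms (assumed shares).** Multiply both rates by the share:

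| Capture | Observed rates | Power |
|---|---|---|
| 100% | 14.0% vs 21.0% | 83% |
| 90% | 12.6% vs 18.9% | 78% |
| 80% | 11.2% vs 16.8% | 72% |
| 70% | 9.8% vs 14.7% | 66% |
| 60% | 8.4% vs 12.6% | 58% |

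**Step 3: unequal capture, no true difference (14% in both arms).** The chance of a significant result in either direction should be 5%:

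| Capture, better vs worse arm | Observed rates | Chance of significance |
|---|---|---|
| 90% vs 80% | 12.6% vs 11.2% | 10.5% |
| 90% vs 70% | 12.6% vs 9.8% | 28.9% |
| 90% vs 60% | 12.6% vs 8.4% | 58.2% |

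For the middle row, d = 0.028, s0 = 0.01995 and s1 = 0.01993. Then (0.028 − 0.0391)/0.01993 = −0.557 and Φ = 0.289. The arm with better capture appears to seek more care, whichever arm that is.

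**Step 4: unequal capture, true 14% (intervention) vs 21% (control).**

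- 90% capture in intervention and 70% in control: 12.6% vs 14.7%. The 7-point difference becomes 2.1 points and power is 16%.
- 90% and 60%: 12.6% in both arms, so the difference disappears.
- The reverse, 70% and 90%: 9.8% vs 18.9%. The difference grows to 9.1 points and is significant 98% of the time.

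The bias can therefore run either way.

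**The case against.** A reader might infer that the plan codes every outside visit as no visit. The documents do not say so. The Aim 1 sentence concerns diagnosis and pathology, and the power section names no data source for appointments. The privacy section gives access to subject-reported information and to the EHR of women who have had a visit for a mole, which could mean that visits are first learned from the women. An undercount is what follows if the described procedures are all there is; it is not a stated rule.

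Nor do the documents show that the survey omits visits. The instrument is not included, and the one-line description is plainly not a full list: read literally, it would omit SSE itself. The consent and HIPAA text is also not available, so whether outside records may be requested cannot be judged.

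Differential capture is a possibility, not a finding. A local provider may be inside the system, biopsy navigation reaches only some intervention women, and the direction is unknown. The 14% and 21% may already be rates as captured, in which case multiplying by a capture share discounts twice. It would also be wrong to say that better intervention capture creates a false result in the plan's direction: 12.6% intervention vs 9.8% control runs opposite to 14% vs 21%.

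These limits stand, but they do not remove the gap. Even if the survey asks about visits, nothing makes those answers a source for this outcome or reconciles them with the EHR. The post-study contact in Study Timelines covers incomplete survey answers and questions raised by the EHR review, and a visit absent from the EHR raises no such question.

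**Conclusion.** The concern holds as a gap in ascertainment. The one record source named is a single system's EHR, care may be sought outside that system in both arms, and no route for capturing such visits is described. The secondary outcome and time to care may be undercounted, and the loss could differ by arm in either direction. The primary SSE outcome is unaffected.

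The size is unknown. On assumed equal capture of 60% to 90%, power falls from 83% to between 58% and 78%. On assumed gaps of 10 to 30 points between arms, the false-positive rate at a true 14% rises from 5% to between about 10% and 58%. These figures illustrate sensitivity and do not estimate what will happen. They rest on a two-sided 5% test, 500 per arm, and 14% and 21% being true rates.

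The point is worth acting on because the remedy is cheap, and outside visits may be hard to recover once follow-up has ended.

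**What to change.** - Unless the survey already does so, put identical items in both arms' monthly survey and in one closing contact at the EHR-review date: any provider visit about a mole, inside or outside Northwestern Medicine, with date, biopsy and result.
- Define the secondary outcome as a visit found from either source.
- Record at baseline whether the woman's usual or skin care is within Northwestern Medicine.
- Report two sensitivity analyses: EHR only, and restricted to women whose usual care is in the system.
- Extend the planned multiple imputation to missing survey answers on visits.

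**Cost.** A few REDCap items, one extra contact and some analysis wording. There are real drawbacks. Outside visits will rest on self-report, and asking may itself prompt visits. With expected retention of at least 60%, survey answers could be missing for up to 40% of women (0.40 × 500 = 200 per arm), perhaps unequally by arm. EHR review does not depend on survey completion, so the EHR-only result should stand beside the combined one.
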